Appendix 2.3. Definition of Protocol Deviations That Relate to Statistical Analyses/Populations

Appendix 3. Data Set Descriptions

Appendix 4. Statistical Methodology Details

Linear Interpolation

Linear interpolation will be employed to provide mean expected standing height values at 6 month interval for children $>$ age 4. The SAS code is as follows:

```
proc expand data=mydata out=LinInterp;
  convert exp_mean=linear / method=join;
  id age;
run;
```

MMRM

MMRM will be used for height growth and arm span-height difference. The SAS code is as follows:

```
proc mixed data=mydata;
  class dose gender month;
  model height = dose month gender age/s;
  random int month / type=un sub=subject;
  lsmean dose;
run;
```

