9.1. Estimands and Statistical Hypotheses

Height Growth Endpoint

Null hypothesis for height growth in this study is that height 12 months post-baseline for children on recifercept is equal to the expected height growth for the achondroplasia reference population based on Merker (2018).³⁰ The alternative hypothesis is that height growth for recifercept-treated participant is greater than the expected growth for achondroplasia reference population based on Merker (2018).³⁰

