9.4.2. Primary Endpoint(s)

Efficacy

The primary efficacy endpoint of change from baseline of height at 12 months will be analyzed using an analysis of variance (ANOVA) model comprising terms for reciferecept dose groups. Change from baseline estimates for height and their corresponding 95% confidence intervals will be provided via least-square means. A Bonferroni adjustment will be applied to the 95% confidence intervals. The population for the primary analysis will be based on the FAS, while the PPAS is the population that will be used for sensitivity analysis.

Safety

The safety data will be summarized in accordance with Pfizer Data Standards. All participants who receive IP (safety population) will be included in the safety analyses. All safety data will be summarized descriptively through appropriate data tabulations, descriptive statistics, categorical summaries, and graphical presentations. Safety endpoints for the study include:

- TEAEs and SAEs;
- Withdrawals from treatment due to AEs.

Change from baseline in laboratory data and vital signs will be additionally summarized. Participant listings will also be produced for these safety endpoints.

PK Study Cohort:

The pharmacokinetic parameters following single dose administration in the PK cohort will be derived from the concentration-time profile as follows:

Parameter	Definition	Method of Determination
AUC _{inf}	Area under the serum concentration time profile from time 0 extrapolated to infinite time.	AUC _{last} + (C _{last} * / k _{el}), Where C _{last} * is the predicted serum concentration at the last quantifiable time point estimated from the loglinear regression analysis.
AUC ₁₆₈	Area under the serum concentration-time profile from 0 to 168 hours.	Linear/Log trapezoidal method.
AUC ₃₆₀	Area under the serum concentration-time profile from 0 to 360 hours.	Linear/Log trapezoidal method.
C _{max}	Maximum serum concentration.	Observed directly from data.
T _{max}	Time for C _{max} .	Observed directly from data as time of first occurrence.
t _{1/2}	Terminal elimination half-life.	Log _e (2)/k _{el} , where k _{el} is the terminal phase rate constant calculated by a linear regression of the loglinear concentration time curve. Only those data points judged to describe the terminal loglinear decline will be used in the regression.

Actual PK sampling times will be used in the derivation of PK parameters.

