2.1.1. Primary Estimand(s)

The primary estimand is defined according to the primary objective and is in alignment with the primary endpoint. It includes the following 4 attributes:

- Population: Patients with achondroplasia, as defined by inclusion/exclusion criteria;
- Variable: Height Growth at 12 months;
- Height Growth = (Observed Change from Baseline in standing height (cm))/(Expected Change from Baseline (cm)[Merker et al, 2018]¹)

- Intercurrent event(s): Withdrawal and all events leading to missing data will be excluded from efficacy analysis and will not have their data imputed;
- Population-level summary: Mean Height growth at 12 months adjusted for age and gender.

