5.1. Hypotheses and Decision Rules

The null hypothesis for primary efficacy analysis is that observed height growth 12 months post-baseline for children on reciferecept is equal to the expected height growth for the achondroplasia reference population based on Merker (2018). The alternative hypothesis is that observed height growth 12 months post-baseline for children on reciferecept is greater than the expected height growth for the achondroplasia reference population based on Merker (2018).

The Bonferroni correction method is used to control the overall familywise error rate of 0.05 for multiple comparisons. The post-baseline estimate will be considered statistically significant at the 1-sided 0.017 level.

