5.2.1. Analyses for Longitudinal Continuous Endpoints

Mixed-effect, repeated measures (MMRM) models will be used. The fixed effects of treatment, visit, treatment-by-visit interaction, age and gender will be included. Visit will be modeled as a categorical covariate. (If the model does not converge then Visit will be modeled as a continuous covariate.) Unstructured covariance matrix will be assumed for the model errors. Compound symmetry covariance matrix will be used if the model with unstructured variance covariance doesn't converge.

When modeling the change from baseline values, the variable for visit will start with the first post-baseline visit. At each visit, estimates of least square mean (LSM) values and the LSM differences between treatment groups will be derived from the model. The corresponding p-values and 95% confidence intervals will also be derived from the model.

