9. APPENDICES

Appendix 1. Summary of Efficacy Analyses

Endpoint	Analysis Type	Population	Data Inclusion and Rules for Handling Intercurrent Events and Missing Data	Analysis Model
Change from baseline to Month 12 in mean standing height	Summary	FAS	Separately for observed data and imputed data.	N/A
	Main analysis	FAS	All data collected will be included regardless of intercurrent events. Missing data will not be imputed.	MMRM with terms time,dose, gender & age
	Sensitivity/supplementary analysis	PPAS	All data collected will be included regardless of intercurrent events. Missing data will not be imputed.	ANOVA
Change from baseline to Month 12 in mean arm span-height difference	Summary	FAS	Separately for observed data and imputed data.	N/A
	Main analysis	FAS	All data collected will be included regardless of intercurrent events. Missing data will be not be imputed.	MMRM with terms time,dose, gender & age
	Sensitivity/supplementary analysis	PPAS	All data collected will be included regardless of intercurrent events. Missing data will not be imputed.	ANOVA

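### The only primary-analysis code averages each dose over Months 3 to 12 instead of testing Month 12 growth, and the plan names several different primary models

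*SAP*

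**What the plan says.** **Target.** SAP 2.1.1 defines Height Growth as observed over expected change from baseline and summarises it as "Mean Height growth at 12 months adjusted for age and gender". SAP Appendix 2.2 gives the same ratio, H. Protocol 9.1 states the null as "height 12 months post-baseline for children on recifercept is equal to the expected height growth", and SAP 5.1 agrees and adds: "The post-baseline estimate will be considered statistically significant at the 1-sided 0.017 level". Neither document writes the number 1, but on the ratio scale the null is mean H = 1 at Month 12.

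**Models offered for that target:**

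- SAP 5.2.1: "The fixed effects of treatment, visit, treatment-by-visit interaction, age and gender will be included". It continues: "At each visit, estimates of least square mean (LSM) values and the LSM differences between treatment groups will be derived from the model". The errors have an unstructured covariance.
- SAP 6.1.1.1 (main analysis): an MMRM on Months 3, 6, 9 and 12 that refers to 5.2.1. It makes age optional and adds a subject and/or time random effect. The response is change relative to the reference, but the LS means to be shown are for change in standing height.
- SAP Appendix 1: "MMRM with terms time,dose, gender & age", with no interaction.
- SAP Appendix 4 (the only code): "model height = dose month gender age/s", then random intercept and month, then LS means for dose alone.
- Protocol 9.4.2: "The primary efficacy endpoint of change from baseline of height at 12 months will be analyzed using an analysis of variance (ANOVA) model", with dose terms only.

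**Data rule.** SAP 6.1.1.1 drops data after discontinuation or rescue. SAP Appendix 1 keeps all collected data. Protocol 9.1.1 sets the estimand regardless of compliance.

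**Per-protocol analysis.** SAP 6.1.1.2 repeats the main method; Appendix 1 says ANOVA.

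**The concern.** The code is the most concrete statement of the primary analysis, and it does not produce the quantity the hypothesis concerns. Without a dose-by-month term the model assumes parallel dose profiles, and a dose LS mean weights the four visits' effects equally. It equals Month 12 H only if H does not change over visits. An effect that builds up is understated and one that wanes is overstated. The default LS-mean test is against 0, which is not the null for a ratio. The response is called `height`, and the same block also has to serve the arm span-height difference.

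The appendices and the SAP body disagree, the protocol names a further model, and no sentence says which governs. Model, data rule and reported estimate could each be chosen after seeing the data and still be called planned.

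**Working it through.** **Inputs.** 15 evaluable per dose, inter-participant variability 0.15 and planned effect +50% (Protocol 9.2); one-sided level 0.05/3 = 0.0167 (SAP 5.1); visits at Months 3, 6, 9 and 12 (SAP 6.1.1.1). *Assumptions:* 0.15 is the SD of H (no unit is given) and also the SD of the visit average; the data are balanced. The documents give no time course for H, so every profile below is illustrative.

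**1. The plan's power figure.** SE = 0.15/√15 = 0.0387. Noncentrality = 0.5/0.0387 = 12.9. Power per dose exceeds 99.99%, so the stated figure of over 90% holds as a lower bound.

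**2. What the code estimates when all doses share a time course.** It is the simple mean of the four visit values, whatever the covariance. For a lag of L months, H(t) = 1 + k·max(0, t − L)/t. If a gain g stops at 6 months, H(t) = 1 + g up to Month 6 and 1 + 6g/t after.

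| Assumed course | H at 3, 6, 9, 12 | Month 12 | Code |
|---|---|---|---|
| Constant | 1.5, 1.5, 1.5, 1.5 | 1.50 | 1.50 |
| 3-month lag | 1.000, 1.333, 1.444, 1.500 | 1.50 | 1.32 |
| 6-month lag | 1.000, 1.000, 1.333, 1.500 | 1.50 | 1.21 |
| 50% gain, stops at 6 months | 1.500, 1.500, 1.333, 1.250 | 1.25 | 1.40 |
| 20% gain, stops at 6 months | 1.200, 1.200, 1.133, 1.100 | 1.10 | 1.158 |
| 3-month lag, small effect | 1.000, 1.100, 1.133, 1.150 | 1.15 | 1.096 |

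**3. Power against H = 1.** Noncentral t, noncentrality (mean − 1)/(SD/√15), 45 − 3 = 42 df, critical value 2.200.

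- Planned effect: a 3-month lag (1.32) gives >99.9%. A 6-month lag (1.21) gives 99.9%, or 99.7% on 14 df, or 96.4% at SD 0.20.
- 20% gain stopping at 6 months: 65% at Month 12; 97% from the code (80% to >99% for SD 0.20 to 0.12). H = 1.10 is not the null, so this is overstatement and not a false positive.
- Lagged H of 1.15: 95% at Month 12; 61% from the code (37% to 81% for SD 0.20 to 0.12).

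**4. Doses with different time courses.** Under dose + month with within-child covariance S, the visit weights are w = S⁻¹1/(1ᵀS⁻¹1). The dose LS mean is the equal mean of the overall visit means plus the w-weighted deviation of that dose. Take three doses: H = 1 throughout; 3-month lag to 1.50; constant 1.50.

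| Covariance | w | Dose LS means |
|---|---|---|
| Compound symmetry | 0.25 each | 1.00 / 1.32 / 1.50 |
| Independent quarterly increments | (0, 0, 0, 1) | 0.94 / 1.44 / 1.44 |
| Fixed height error divided by expected growth | (−0.1, 0, 0.3, 0.8) | 0.93 / 1.46 / 1.43 |

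With dose-by-month, the Month 12 values are 1.00 / 1.50 / 1.50 under any S. Except under compound symmetry, a dose with no effect is shifted by the other doses. The shift can also go upward. Take two doses at H = 1 throughout and one with the 50% gain that stops at 6 months. The overall visit means are 1.167, 1.167, 1.111 and 1.083, averaging 1.132. With w = (0, 0, 0, 1) each no-effect dose reads 1.132 + (1 − 1.083) = 1.049.

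**5. If `height` meant change in cm.** Under linear growth the four-visit mean is (0.25 + 0.50 + 0.75 + 1)/4 = 62.5% of the Month 12 change.

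**6. Covariance coding.** A random intercept plus four month effects, unstructured, needs 5·6/2 = 15 parameters plus a residual, 16 in all. A 4×4 within-child covariance identifies 4·5/2 = 10.

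**The case against.** The strongest reply is that the SAP body already has the right analysis. Section 5.2.1 includes the interaction, and 6.1.1.1 refers to it and asks for LS means at every post-baseline visit, Month 12 among them. The code looks like a template: placeholder dataset, generic response name, one block for two endpoints. This narrows the conflict to body text against Appendices 1 and 4, but it does not settle it. Two places in the SAP omit the term, and nothing gives the body text precedence.

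Second, the time courses are invented. That is true. The documents supply none, constant H gives no bias, and the planned effect is detected either way. The figures show the possible size of the error and do not predict it.

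Third, ANOVA and MMRM are close in practice. With complete data, an unstructured model with dose-by-month reproduces the Month 12 ANOVA means apart from covariate adjustment. Whether the switch is a major modification needing an amendment (Protocol 9, SAP 2) is arguable. The protocol still says ANOVA, however, and Amendment 1 was used to clarify ANOVA over ANCOVA.

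Fourth, few post-discontinuation data may exist, because Protocol 7.1 has children leave the study on definitive discontinuation. Protocol 7.2.1 says those who ask to stop treatment stay in follow-up. Those passages must themselves be reconciled, so the data-rule conflict is not empty.

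**Conclusion.** The concern holds and should be corrected before the primary analysis is run. The textual conflict is certain: the printed code and the Appendix 1 term list do not yield the Month 12 mean of H, and no test against 1 is coded.

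The numerical effect depends on how H moves between Months 3 and 12. It is nil if H is constant. In the shared-course examples the error ranges from 0.05 to 0.29 on the ratio scale (1.15 read as 1.096; 1.50 read as 1.21). Power at the planned effect is not at risk. For smaller effects the conclusion can change in either direction. These sizes rest on an SD of 0.15 for H, balanced data and the assumed profiles.

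Lesser points follow from the same lack of alignment. The displayed intervals are unadjusted 95% in SAP 6.1.1.1 but Bonferroni-adjusted in Protocol 9.4.2, which matters for error control only if intervals are used to decide. The +50% in Protocol 9.1.1 could be misread as the null value. Expected height is interpolated only to a 6-month grid (SAP Appendix 2.2), although H is also needed at Months 3 and 9.

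**What to change.** Replace the Appendix 4 block for height growth with one whose default test addresses the null:

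```
class subject dose gender month;
model H_minus_1 = dose month dose*month gender age;
repeated month / subject=subject type=un;
lsmeans dose*month / cl alpha=0.0333;
```

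Then:

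- State the decision rule: for each dose, the Month 12 LS mean of H − 1 is tested against 0 at one-sided 0.05/3 and shown with the matching two-sided interval, 1 − 2 × 0.05/3 = 96.67%.
- State the degrees-of-freedom method, and whether the convergence fallbacks in 5.2.1 are kept.
- Interpolate expected height to each child's age at each visit.
- Give the arm span-height difference its own code.
- Align Protocol 9.4.2 and SAP 6.1.1.1, 6.1.1.2 and Appendix 1 to this model, including whether age is in it, the scale of the reported LS means and the per-protocol method.
- Adopt one intercurrent-event data rule across Protocol 9.1.1, SAP 6.1.1.1 and Appendix 1.
- Say in Protocol 9.1.1 that +50% is the design effect of Section 9.2 and not the null.

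The cost is SAP text and code plus a protocol wording change. No extra participants or data are needed.

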6. ANALYSES AND SUMMARIES

6.1. Primary Endpoint(s)

6.1.1. Increase in height growth above expected in reference population

6.1.1.1. Main Analysis

- Estimand strategy: Hypothetical ([Section 2.1.1](#)).
- Analysis set: FAS ([Section 4](#)).
- Analysis methodology: Change from baseline relative to Merker (2018) will be analyzed using MMRM including data from Months 3, 6, 9, and 12 with gender (and possibly age) as a covariate, subject (and/or time) as a random effect and an unstructured covariance matrix ([Section 5.2.1](#)).
- Intercurrent events and missing data: Data after study drug discontinuation and rescue will be excluded; intermediate missing values will not be imputed.
- The sample size, mean, standard deviation, median, minimum, and maximum at the baseline and postbaseline visits for observed standing height and change from baseline will be presented for each treatment arm.
- The least-squares (LS) means, the 95% confidence interval for the LS means, the difference between the LS means for each pair of treatment groups, and the corresponding 95% confidence interval will be presented for change from baseline in standing height for all postbaseline visits.

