Appendix 2.2. Endpoint Derivations

Height Growth

The primary efficacy endpoint is H defined by the following:

$$H_{ijkl} = \frac{Y_{ijkl} - Y_{i0kl}}{Z_{jl} - Z_{0l}},$$

where Y_{ijkl} is the observed standing height for the i th subject, at month j on dose k with gender factor l ($j=0$ denotes baseline measurement) and Z_{jl} is the mean expected standing height based on Merker for subject i 's age.

Mean expected standing height from Merker is sorted by 6 months up to age 4, while means expected values for children > 4 years are sorted per annum. Linear interpolation will be employed to calculate mean expected values so that mean standing height are sorted at 6 month intervals for children > 4 years. SAS code for the linear interpolation calculation will be provided in Appendix 4.

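### The primary MMRM code is over-parameterized (16 covariance parameters for 10), gives no Month 12 estimate by dose, and its compound-symmetry fallback would misstate the Month 12 standard error

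*SAP*

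**What the plan says.** SAP 5.2.1 sets out the general longitudinal model: treatment, visit, treatment-by-visit interaction, age and gender as fixed effects. On covariance it says: "Unstructured covariance matrix will be assumed for the model errors". It names two responses to non-convergence without ranking them. One is "If the model does not converge then Visit will be modeled as a continuous covariate". The other is "Compound symmetry covariance matrix will be used if the model with unstructured variance covariance" fails to converge.

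SAP 6.1.1.1 applies this to the primary endpoint as an "MMRM including data from Months 3, 6, 9, and 12", but adds "subject (and/or time) as a random effect and an unstructured covariance matrix". SAP 6.2.1.1 (arm span to height difference) and 7.2 (interim, Months 3 and 6) use the same wording.

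The Appendix 4 code for both endpoints has "class dose gender month" and "random int month / type=un sub=subject". It has no REPEATED statement, dose-by-month term or degrees-of-freedom method, and its LS means request names dose alone.

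The scale of the response is not settled. Appendix 2.2 says "The primary efficacy endpoint is H defined by the following" and gives observed change divided by expected change. Yet 6.1.1.1 promises LS means for change in standing height, Appendix 1 lists that change as the endpoint, and the coded response is a variable called height.

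**The concern.** Three things do not fit together.

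- **Code against text.** An unstructured matrix on the errors and an unstructured matrix on a random intercept plus four random month effects are different specifications. The second cannot be uniquely estimated from four visits.
- **Code against the question.** The hypothesis in SAP 5.1 concerns growth at 12 months. LS means by dose, without an interaction, average over Months 3 to 12.
- **Fallback against the endpoint.** Compound symmetry imposes one variance on all visits. For a ratio whose denominator grows over the year, height measurement error weighs much more at Month 3 than at Month 12. For a change in cm, spread normally increases with time. A common variance suits neither.

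At stake are the Month 12 interval for each dose and the one-sided 0.017 test in SAP 5.1. Protocol 6.3 blinds only the anthropometrist, so a choice between unranked fallbacks could be made with dose known.

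**Working it through.** **1. The plan's own figure.** Protocol 9.2 gives n = 15 per dose, variability 0.15, effect +50% and one-sided 0.017. SE = 0.15/√15 = 0.0387, and 0.5/0.0387 = 12.9, far above the critical value of about 2.12. Power is close to 100%, consistent with the stated figure of over 90%.

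**2. Parameter count.**
- Four visits: random intercept plus four month effects give a 5 × 5 matrix, 5 × 6/2 = 15, plus one residual = **16**. The 4 × 4 marginal covariance has 4 × 5/2 = **10** distinct elements. The map from parameters to elements has rank 10, so 6 are redundant.
- Interim, two visits: 3 × 4/2 + 1 = **7** against 2 × 3/2 = **3**.

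**3. Does redundancy alone change the answer?** The 16-parameter likelihood was maximized from five starting points, with a general optimizer rather than SAS. Each run reached the unstructured maximum with Month 12 SD 0.150, while the intercept and residual variances differed between runs. The components are not unique, but the Month 12 SE can be unaffected.

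**4. Compound symmetry, if triggered.** This step uses the SAP 5.2.1 model with treatment-by-visit interaction and complete data. The compound-symmetry variance is then the mean of the four visit variances, so

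SE multiplier at Month 12 = √(mean visit variance / Month 12 variance).

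Inputs:
- From the documents: 0.15, given without unit or time point and taken here as the Month 12 SD of H.
- Assumed: height error SD *e* per measurement, expected growth *g* cm/year, linear growth within the year, and a true ratio constant over visits.

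The share of Month 12 variance due to measurement error is f = (2e²/g²)/0.0225.

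- Ratio scale: visit variance is proportional to (1 − f) + f(12/t)². The mean of (12/t)² over 3, 6, 9 and 12 is 5.694, so the multiplier is √(1 + 4.694f).
- cm scale: visit variance is proportional to (1 − f)(t/12)² + f. The mean of (t/12)² is 0.469, so the multiplier is √(0.469(1 − f) + f).

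| e (cm), g = 5 | f | Multiplier, ratio H | Multiplier, cm change |
|---|---|---|---|
| 0.2 | 0.142 | 1.29 | 0.74 |
| 0.3 | 0.320 | 1.58 | 0.80 |
| 0.4 | 0.569 | 1.92 | 0.88 |

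At e = 0.3 the SD of H is about 0.36, 0.21, 0.17 and 0.15 at Months 3, 6, 9 and 12. Simulation (3 doses × 15, 3,000 runs) gave ratio-scale multipliers of 1.30, 1.59 and 1.92. Over e = 0.1 to 0.4 and g = 4 to 6, the range is 1.06 to 2.27 for the ratio and 0.69 to 0.97 in cm.

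**5. Consequences (normal approximation, z = 2.128 for 0.05/3).** With balanced data the estimate does not move; only its reported SE changes.
- Ratio scale, interval: the 95% half-width is 1.96 × 0.0387 = 0.076. Multipliers of 1.3 and 1.9 make it 0.099 and 0.144.
- Ratio scale, power: Φ(δ/0.0387 − 2.128 × multiplier). For +15%, δ/0.0387 = 3.873. Correct SE: Φ(1.745) = 96%. Multiplier 1.58: Φ(0.51) = 69%. For +50% at 1.92: 12.9 − 4.1 = 8.8, so power stays near 100%.
- cm scale, error rate: 1 − Φ(2.128 × multiplier). At 0.74 this is 1 − Φ(1.57), about 0.06. At 0.88 it is 1 − Φ(1.87), about 0.03. The nominal level is 0.017.

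**6. Continuous-visit fallback.** Put into the coded RANDOM line, it gives a random intercept and slope, whose variance can change over time. The Month 12 multiplier is 1.05 to 1.20 on the ratio scale and 1.00 in cm, for e = 0.2 to 0.4.

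**The case against.** The best defence is that the fallback may never be used. Redundant parameters do not guarantee non-convergence, and step 3 shows that the fit can still reach the unstructured solution. That stands: a reader might infer from the count of 16 against 10 that the Month 12 intervals will come out too wide, and the documents do not support that. Compound symmetry applies only after declared non-convergence. Even then, too wide holds only for the ratio; in cm the error reverses.

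A reader might also infer that both fallbacks impose equal variance. They do not. In SAP 5.2.1 continuous visit changes a covariate and leaves the error matrix unstructured; in the coded model it allows variance to change with time.

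The multipliers are not document figures. Neither document gives height error, yearly expected growth or SD by visit, and the reference table is described only on a 6-month grid, so 3-month denominators are an assumption too. The ratio-scale figures also do not carry over to the arm span difference, although the coding defects do, since Appendix 4 uses the same code.

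Finally, Protocol 9.4.2 specifies an ANOVA of 12-month change, which needs no covariance across visits. That is a separate conflict between protocol and SAP. It does not repair the SAP model, but it shows that a Month 12-only analysis is a natural last resort.

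**Conclusion.** The point holds as a specification defect in the primary model. Three parts need no outside figure: 16 parameters for 10 estimable elements (7 for 3 at the interim), a mismatch with the error-side matrix in SAP 5.2.1, and no Month 12 estimate by dose from the code as written.

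The effect on the standard error is conditional. If compound symmetry is triggered, the Month 12 SE is about 1.3 to 1.9 times the correct value for H and about 0.74 to 0.88 times in cm. Both ranges assume 0.2 to 0.4 cm height error, 5 cm/year and a Month 12 SD of H of 0.15.

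The trial is not underpowered for its design effect because of this. The harm is to the reported intervals, to power for moderate effects on the ratio scale (+15%: 96% to 69% at 0.3 cm), and to the one-sided 0.017 level if cm change is analyzed.

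**What to change.** - **SAP 6.1.1.1, 6.2.1.1, 7.2 and Appendix 4:** remove the RANDOM statement and the wording that makes subject and/or time a random effect. Use `repeated month / subject=subject type=un` with a named degrees-of-freedom method, for example Kenward-Roger.
- **Appendix 4:** add `dose*month` to the model and request LS means for `dose*month`, so that Month 12 is estimated for each dose.
- **SAP 5.2.1:** replace homogeneous compound symmetry with an ordered list of heterogeneous-variance structures (for example TOEPH, ARH(1), CSH), ending with a Month 12-only analysis. If continuous visit is kept, state its place in the order.
- **SAP 6.1.1.1, Appendix 1 and Appendix 4:** state that the height-growth response is H, and align the LS means and code with it.

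The cost is a few lines of SAP text and code, before database lock. No new data are needed.
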